#### Primary Objective

• To evaluate safety and tolerability and preliminary anti-leukemia activity (Dohner, et. al 2010)22 of PF-06747143 in combination with standard intensive chemotherapy (ie,

cytarabine and daunorubicin; D/C 7+3) in patients with newly diagnosed fit treatment naïve AML patients (Cohort 1) or with standard dose of decitabine or azecitidine in newly diagnosed unfit treatment naïve AML patients (Cohort 2) or PF-06747143 as a single agent ((Cohort 3) if data warrants).

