#### **Primary Endpoints**

 Adverse Events as characterized by type, frequency, severity (as graded by National Cancer Institute Common Terminology Criteria for Adverse Events (NCI CTCAE) v. 4.03), timing, seriousness, and relationship to study therapy;

- Laboratory abnormalities as characterized by type, frequency, severity (as graded by NCI CTCAE v.4.03) and timing;
- Preliminary evidence of anti-leukemia activity including objective disease response; as assessed using the standardized response criteria including objective response rate (ORR), duration of ORR, and relapse free survival (RFS).(Ref 2)

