#### 6.2. 'PER PROTOCOL' Analysis Set

The per protocol analysis set includes all enrolled patients who receive at least one dose of study treatment at the dose level of MTD and who do not have major treatment deviations during first cycle. Patients with major treatment deviations in Cycle 1 are not evaluable for the MTD assessment and may be replaced. Major deviations include failure to satisfy major entry criteria (eg, confirmation of the target disease population; signed informed consent), administration of less than 3 out of the 4 doses in Cycle 1 or 80% of the planned Cycle 1 dose (provided that the reduction is not due to toxicity attributable to PF-06747143) or use of

other anti-cancer/anti-leukemia treatments during the active treatment and disease follow up phases other than as defined/allowed in this protocol.

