#### 6.6. Protocol Deviations

All deviations will be listed in the CSR. Major treatment deviations include, but are not limited to, less than 80% of the planned Cycle 1 PF-06747143 dose provided the reduction/omission is not due to treatment-related toxicity. Subjects with major Cycle 1 treatment deviations are not evaluable for MTD.

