#### 9.2.2. Secondary Analyses

#### 9.2.2.1. Efficacy Analysis

In this Phase 1 study efficacy is a secondary objective. Note that the efficacy analysis is to be conducted by malignancy for patients in the MTD expansion cohorts who are in the Safety Analysis Set and have baseline disease assessment and at least one post-baseline disease assessment. In the event that a large number of patients in the escalation portion of the study have the same malignancy, the efficacy analysis may be conducted.

Summary tables of best Overall Response Rate, Progression Free Survival, and Overall Survival will be provided overall and by malignancy. Efficacy listings will be provided that include best response, first CR/PR date, last date with CR or PR, most recent date without progression, progression date, death date, date of first response and last tumor assessment date, etc.

A response rate overall for Part 1 dose escalation and response rates by low, medium, and high dose groups may be presented.

The following table provides an overview of the efficacy analysis.

**Endpoint Analysis Set** Interpretation **Statistical** Model/ Missing Method Covariates/ Data Strata By dose range/ Overall Per Protocol, Exact CI Censored Secondary response expansion malignancy per Section Analysis 11.2 cohorts, etc. Progression Per Protocol, Kaplan-By malignancy Censored Secondary Free Survival expansion per Section Meier Analysis (PFS) cohorts 11.2 Per Protocol, By malignancy Censored Secondary Time to Kaplan-Progression expansion Meier per Section Analysis cohorts 11.2 (TTP) Duration of Per Prtocol, By malignancy Censored Secondary Kaplan-Response (DR) expansion Meier per Section **Analysis** cohorts 11.2

**Table 2.** Overview of Efficacy Analysis

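### Part 2 response and relapse-free survival are primary endpoints, but SAP Section 9.2.2.1 treats efficacy as secondary, names two different response sets, gives ORR no usable missing-data rule, specifies no output by cohort, and leaves RFS out of Table 2 and Appendix 2

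*SAP*

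**What the plan says.** **Status.** The Part 2 primary objective (Section 2.3.3) begins "To evaluate safety and tolerability and preliminary anti-leukemia activity". The Part 2 primary endpoints (Section 2.4) include "objective response rate (ORR), duration of ORR, and relapse free survival (RFS". In Part 1 the same activity endpoints are secondary (Sections 2.3.1 and 2.3.2). Section 9.2.2.1, which is mainly about the expansion cohorts, opens: "In this Phase 1 study efficacy is a secondary objective". All four rows of Table 2 (overall response, PFS, TTP, duration of response) are marked as secondary analyses. Section 9.2.1, the primary analysis, covers DLT only.

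**Analysis set.** The text of Section 9.2.2.1 takes expansion-cohort patients in the Safety Analysis Set who "have baseline disease assessment and at least one post-baseline disease assessment". Table 2 gives Per Protocol. Its cells run together in the text at hand, but the response row can still be read: "Overall Per Protocol, Exact CI Censored Secondary response". Section 6.2 limits Per Protocol to patients dosed at the MTD level with no major Cycle 1 treatment deviation.

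**Missing data and strata.** The response row pairs an exact interval with censoring under Section 11.2. Summaries are planned overall and by malignancy; the response row adds dose range.

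**RFS.** Section 8.2 places the censoring rules for time-to-event endpoints in Appendix 2. Appendix 2 has Table 4 (PFS and duration of response) and Table 5 (TTP). Section 7.1 refers to a section 7.6 in connection with RFS; the SAP as shown has no such section.

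**The concern.** A SAP should let two programmers reach the same primary estimate independently. Here, one who follows the text of Section 9.2.2.1 and one who follows Table 2 start from different patients. Neither finds a rule for a patient who has no response assessment.

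The patients at issue are informative. In AML some patients may die before the first marrow assessment. Section 11.4 counts such deaths as Treatment Failure, and Table 4 counts death before the first planned assessment as a PFS event. A set that leaves them out raises the response rate and discards PFS events that the plan itself provides for.

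Two further gaps concern what is reported. Cohort 1 (fit, untreated, with 7+3), Cohort 2 (unfit, untreated, with a hypomethylating drug) and Cohort 3 (relapsed or refractory, single agent) differ in population and regimen, yet no efficacy output is specified for each. RFS is a primary endpoint with no assigned analysis set and no censoring rule.

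**Working it through.** The SAP gives no power, precision or target figure for Part 2 efficacy, so there is none to reproduce. The check is a comparison of passages, with a small calculation for scale.

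**Side by side**

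| Item | Sections 2.3.3, 2.4, 6, 8.2, 11 | Section 9.2.2.1 and Table 2 |
|---|---|---|
| Part 2 efficacy | Primary | Secondary, parts not separated |
| Response set | None named as main | Text: Safety Set with an assessment. Table 2: Per Protocol |
| Death before first assessment | Treatment Failure (11.4); PFS event (Table 4) | Not addressed |
| Missing response | Section 11.2 has only time-to-event rules | Censored per Section 11.2 |
| Grouping | Three distinct cohorts, one disease | By malignancy; response also by dose range |
| RFS | Primary; rules said to be in Appendix 2 | No row, and no rule in Appendix 2 |

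**How the sets treat early deaths.**
- *Text set:* a patient who dies before any post-baseline assessment is out, unless a Treatment Failure entry on the response CRF counts as an assessment. The SAP does not say.
- *Per Protocol:* a patient who dies during Cycle 1 may fall short on planned dose. Three of four weekly doses is 3/4 = 75%, below the 80% limit in Section 6.2. Whether doses not given because of death are a deviation is not stated.
- *mITT (Section 6.4.1):* keeps treated patients with a baseline assessment who progress or die before the first assessment, but is offered only for interim analyses and conference presentations.

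**Scale.** Inputs: n = 30, the maximum for each of E1 and E2 (Sections 2.2.2.1 and 2.2.2.2). Assumed: 12 responders; 3 or 6 patients dropped; all dropped patients are non-responders. The reference is an all-treated denominator.

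If a fraction d of treated patients is dropped, ORR is multiplied by 1/(1 − d): 30/27 = 1.11 for 3 of 30, and 30/24 = 1.25 for 6 of 30.

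| Dropped | ORR | Exact 95% CI |
|---|---|---|
| 0 | 12/30 = 40.0% | 22.7 to 59.4 |
| 3 | 12/27 = 44.4% | 25.5 to 64.7 |
| 6 | 12/24 = 50.0% | 29.1 to 70.9 |

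Varying the assumed responders from 6 to 18, the increase runs from 2 points (6/30 = 20.0% to 6/27 = 22.2%) to 15 points (18/30 = 60.0% to 18/24 = 75.0%). If no one is dropped it is zero.

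**The case against.** The strongest reply is that little turns on this. The study has no hypotheses, no numeric rule uses Part 2 ORR, and the label changes no calculation. Section 9.1 already gives methods for rates and time-to-event data, and the entries on malignancy and censoring look like template carry-over. That limits the harm to reported estimates, but it does not say which patients form the denominator.

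A reader might also infer more than the documents support:

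- *That the 40% to 50% shift is the gap between the text and Table 2.* It is not. It compares an all-treated denominator, which neither place names, with a reduced one. Both SAP sets could lose the same early deaths. Their difference depends on how many assessed patients have a Cycle 1 deviation or were not dosed at the MTD level, and the SAP gives no basis for that number. Per Protocol could also exclude responders.
- *That Per Protocol certainly removes early leukemia deaths.* Section 6.2 lists "administration of less than 3 out of the 4 doses in Cycle 1 or 80% of the planned Cycle 1 dose" as a major deviation, but does not say that doses missed through death count.
- *That deaths from backbone chemotherapy fall between two exemptions.* Section 6.2 has "provided that the reduction is not due to toxicity attributable to PF-06747143"; Section 6.6 has "less than 80% of the planned Cycle 1 PF-06747143 dose provided the reduction/omission is not due to treatment-related toxicity". The wordings differ, but any effect on ORR is inference and arises only if Per Protocol governs.
- *That the cohorts will be pooled.* The SAP does not say so. Sections 2.2 and 2.2.2.3 treat them separately, and Table 2 refers to expansion cohorts. The defect is only that no by-cohort output is specified.
- *That RFS is undefined in the study.* The SAP ties RFS to a cited guideline and to a section 7.6 that may belong to the protocol. What stands is that Appendix 2 lacks the rule Section 8.2 says is there, and Table 2 has no row.

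The SAP's authors did consider early deaths, as the mITT set shows. They did not assign that set to the final analysis.

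**Conclusion.** The point holds and should be fixed. The conflict over the Part 2 label, the two response sets, the unusable missing-data entry, the one-level stratum and the missing RFS entries can all be read directly from the SAP. That either set would lose early deaths is possible but not certain: it depends on what counts as an assessment and what counts as a deviation.

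The size is therefore only illustrative. With 12 of 30 responders assumed, ORR rises from 40% to 44% or 50% if 3 or 6 non-responders are left out, and not at all if none are. The consequence is confined to how primary Part 2 estimates are reported and read; no test or numeric decision rule is affected.

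**What to change.** 1. In Section 9.2 and Table 2, label Part 2 ORR, duration of response and RFS as primary. Keep Part 1 efficacy secondary.
2. Name one main set for Part 2 ORR: all treated patients in each cohort, with those lacking a post-baseline assessment counted as non-responders. Put that rule in the response row in place of censoring.
3. Keep the assessment-evaluable or Per Protocol set as a sensitivity analysis, stating whether a Treatment Failure entry is an assessment and whether doses missed through death are a deviation.
4. For PFS, use a set that retains the early deaths Table 4 counts as events.
5. For Part 2, replace the malignancy grouping with cohort.
6. Add RFS to Table 2 and Appendix 2 with its analysis set, events and censoring, reconciled with the Relapse category in Section 11.4 and with the protocol definition. Correct the pointer to section 7.6.

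The cost is SAP wording and table shells, with no new data. Reported ORR may be somewhat lower than in a reduced set, and by-cohort intervals will be wider than one for a single overall figure.

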#### 9.2.2.2. Pharmacokinetics Analyses

#### **Pharmacokinetic Parameters**

To assess the pharmacokinetics of PF-06747143, PK parameters detailed in Section 7.3 will be listed and summarized for subjects in the PK analysis set (as defined in Section 9.1 of the protocol or Section 6.2 in this document Missing values will be handled as detailed in Section 8. Each PK parameter will be summarized by dose and cycle and will include the set of summary statistics as specified in the table below:

**Table 3.** PK Parameter Summaries

Parameter	Summary statistics
AUC last ,	N, arithmetic mean, median, cv%, standard deviation, minimum,
$\mathrm{AUC}_{\infty}$ ,	maximum, geometric mean
$AUC_{\tau}$ , $C_{max}$ ,	
CL, V ss , and	
R ac	
t 1/2	N, arithmetic mean, median, cv%, standard deviation, minimum,
	maximum
$T_{max}$	N, median, minimum, maximum

There will be 1 summary table presenting all PK parameters. This will include data from all cohorts and will be summarized by dose group and cycle.

To assess the relationship between the PK parameters and dose, dose normalized  $AUC_{\infty}$ ,  $AUC_{last}$ ,  $AUC_{\tau}$ , and  $C_{max}$  will be plotted against dose (using a logarithmic scale), and will include individual subject values and the geometric means for each dose. Geometric means

will have a different symbol than the individual values. The values will be dose normalized (to a 1 mg/kg dose) by dividing the individual values and raw geometric means by dose. A footnote will be added to the plots to indicate that geometric means are presented are presented on the plot.

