#### **Secondary Objectives**

- To characterize the single and multiple dose PK of PF-06747143 in combination with standard intensive cytarabine and daunorubicin 7+3 therapy in newly diagnosed fit treatment naïve AML patients or with standard dose of decitabine or azacitidine in newly diagnosed unfit treatment naïve AML patients;
- To collect PF-06747143 drug concentration data in patients from the dose expansion cohorts for evaluation of population PK;
- To evaluate the immunogenicity of PF-06747143 following repeated administration.

#### 2.4. Endpoints – Part 2

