#### PK analysis sets

The PK parameter analysis population is defined as all enrolled patients treated who have sufficient information to estimate at least 1 of the PK parameters of interest. The PK concentration population is defined as all patients who receive PF-06747143, have no major deviations affecting the PK assessment, and have at least one post-dose concentration measurement.

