#### 7.3. PK Endpoints

Serum pharmacokinetic parameters including the maximum concentration (Cmax), time to maximum concentration (Tmax), and area under the concentration versus time curve (AUClast, AUC $\tau$ ) for PF-06747143 will be estimated using non compartmental analysis. If data permit, area under the concentration versus time curve to infinity (AUCinf), terminal elimination half life (t1/2), clearance (CL), apparent volume of distribution (Vss), and accumulation ratio (Rac) will be also estimated. The PK parameters will be summarized descriptively by dose, cycle and day.

PF0-06747143 concentrations will be summarized descriptively (n, mean, SD, coefficient of variation(CV), median, minimum, maximum, geometric mean and its associated CV) by dose, cycle, day and nominal time. Individual patient and median profiles of the concentration time data will be plotted by dose, cycle and day (single dose and steady state) using nominal times. Individual and median profiles will be presented on both linear linear and log linear scales.

Dose normalized AUCinf (AUC $\tau$  at steady state), and Cmax will be plotted against dose (using a logarithmic scale) by cycle and day. These plots will include individual patient values and the geometric means for each dose. These plots will be used to help understand the relationship between the PK parameters and dose.

The observed accumulation ratio will be summarized descriptively. Each will be analyzed after natural log transformation using a one way analysis of variance with a single term for dose. The means and 90% confidence intervals (CIs) obtained from the model will be back transformed to provide means and 90% CIs for the accumulation for each dose.

Trough concentrations will be plotted for each dose using a box whisker plot by cycle and day within cycle in order to assess the attainment of steady state.

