#### **Pharmacokinetic Concentrations**

To assess the PK profile of PF-06747143, total antibody and unconjugated payload, PK concentrations will be listed, summarized and plotted for subjects in the PK analysis set (as defined in Section 7.3) Presentations for PF-06747143, total antibody and unconjugated payload will include:

- a listing of all concentrations sorted by dose, subject ID, day and nominal time post dose. The listing of concentrations will include the actual times. Deviations from the nominal time will be given in a separate listing.
- a summary of concentrations by dose, day and nominal time post dose, where the set of statistics will include n, mean, median, standard deviation, coefficient of variation (cv) and the number of concentrations above the lower limit of quantification.
- a plot of mean concentrations against nominal time postdose by dose (based on the summary of concentrations by dose and time postdose), preferably with all doses also on the same graph.
- a plot of median concentrations against nominal time postdose by dose (based on the summary of concentrations by dose and time postdose), preferably with all doses also on the same graph.
- a log-linear plot of mean concentrations against nominal time postdose by dose (on the same plot), preferably with all doses also on the same graph.
- a log-linear plot of median concentrations against nominal time postdose by dose (on the same plot), preferably with all doses also on the same graph.
- plots (linear and log scale) of individual concentrations against actual time postdose.

The length of time used for the x-axes of these plots will be decided on review of the data, and will depend on how long PK concentration is quantifiable in the matrix.

In addition to the above, a median plot (linear and log scale) of the predose concentrations at each cycle against day will be provided for each dose, on the same plot, in order to assess the attainment of steady-state. Individual subject profiles will also be plotted.

For summary statistics and mean/median plots by sampling time, the nominal PK sampling time will be used, for individual subject plots by time, the actual PK sampling time will be used.

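### No planned PK summary separates the regimens: single-agent and both combination cohorts share a row at any common dose, although PK in combination is a Part 2 secondary objective

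*SAP*

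**What the plan says.** The Part 2 secondary objectives (SAP Section 2.3.3) include this one: "To characterize the single and multiple dose PK of PF-06747143 in combination with standard intensive cytarabine and daunorubicin 7+3 therapy" in fit patients, "or with standard dose of decitabine or azacitidine in newly diagnosed unfit treatment"-naïve patients. Section 2.4 lists the PK parameters as Part 2 secondary endpoints.

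The planned outputs are grouped as follows.

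- **Parameters, Section 7.3:** "The PK parameters will be summarized descriptively by dose, cycle and day".
- **Parameters, Section 9.2.2.2:** "Each PK parameter will be summarized by dose and cycle". There is one table for all parameters: "This will include data from all cohorts and will be summarized by dose group and cycle".
- **Concentrations, Section 9.2.2.2:** "a summary of concentrations by dose, day and nominal time post dose", with mean and median plots by dose.
- **Dose-normalised plots, Section 9.2.2.2:** these show "individual subject values and the geometric means for each dose".
- **Accumulation ratio, Section 7.3:** a one-way ANOVA on the log scale whose only term is dose.

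The PK parameter population (PK analysis sets, under Section 6.2) is "all enrolled patients treated who have sufficient information to estimate at least 1 of the PK parameters of interest". It is not divided by part or cohort. Section 7.5 names no covariates.

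**The concern.** Part 1 gives the drug alone to patients with relapsed or refractory AML, and 10 mg/kg is one of its levels (Section 2.1.1, Table 1). Part 2 starts both combination cohorts at 10 mg/kg: with 7+3 in fit, untreated patients and with azacitidine or decitabine in unfit, untreated patients (Sections 2.2, 2.2.2.1 and 2.2.2.2). A table split only by dose and cycle puts three regimens, in three populations, on one line.

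Two things are at stake. First, the objective on PK in combination has no summary that matches it. Second, the dose-normalised plots are there to help understand how exposure changes with dose. If one dose level is mostly combination data while the others are single agent, a step at that level could reflect dose, backbone or population, and the geometric means cannot say which.

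**Working it through.** **1. Is there a split anywhere?** The groupings are dose, cycle and day (Section 7.3), dose and cycle (parameter table), dose, day and nominal time (concentrations) and dose alone (plots and ANOVA). None names part, cohort or backbone. By contrast, Section 7.2.8 summarises ECG data by treatment as well as dose, so the SAP can make the distinction and does not make it for PK.

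**2. Reproducing the Part 2 size.** Inputs: up to 30 in each combination expansion cohort, a lead-in of about 3-6 in each, and 15-30 in the optional single-agent Cohort 3 (Sections 2.2 to 2.2.2.4).

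- Low: 30 + 30 + 2×6 + 15 = 87
- High: 30 + 30 + 2×6 + 30 = 102

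This matches the 87-102 of Section 5, so lead-ins of 6 are counted in addition to the 30s.

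**3. Upper bound for the 10 mg/kg row.** Assume both cohorts full, lead-ins of 6, no dose change and every patient evaluable for PK. Combination patients = 2×(6 + 30) = 72. Section 5 expects 2-4 single-agent patients per dose and at least 9 at the MTD.

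| Single agent | Share of row with 72 combination patients | Share with 60 (expansion only) |
|---|---|---|
| 2 | 2/74 = 2.7% | 2/62 = 3.2% |
| 3 | 3/75 = 4.0% | 3/63 = 4.8% |
| 4 | 4/76 = 5.3% | 4/64 = 6.3% |
| 9 | 9/81 = 11.1% | 9/69 = 13.0% |

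**4. What pooling could do to the geometric mean.** The SAP gives no exposure ratio between regimens, so the ratios here are assumptions. With ratios r1 and r2 (combination over single agent), n1 and n2 combination patients and N in the row, the pooled mean relative to single agent is

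G = exp[(n1 ln r1 + n2 ln r2)/N].

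With n1 = n2 = 36 and N = 75:

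- r1 = r2 = 1: G = 1.00
- r1 = r2 = 0.8: G = exp(72×ln 0.8/75) = 0.81
- r1 = r2 = 1.25: G = 1.24
- r1 = r2 = 0.7 or 1.43: G = 0.71 or 1.41
- r1 = 0.8, r2 = 1.25: G = 1.00. Equal cohorts with opposite effects cancel in the pooled mean.

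**5. Away from the upper bound.** Suppose, as an assumption, that only 6 patients per combination cohort yield parameters. The row is then 12 + 3 = 15, of which 12/15 = 80% are on a combination. A common ratio of 0.8 gives G = exp(12×ln 0.8/15) = 0.84. The mix is less extreme, but the row is still mainly combination data.

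**The case against.** The case for leaving the plan alone has several parts.

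- **The data remain separable.** Parameters and concentrations are listed, and individual profiles are plotted. A reader might infer from the single table that the combination objective cannot be answered or that any backbone effect is hidden. The documents do not support that: a split by regimen could be made afterwards. What stands is that none is planned. Section 2.3.3 also has a population PK objective, where such effects might be examined, but the SAP does not describe that analysis.
- **The plots may not be distorted.** The sentence on all cohorts concerns the table. Pooling in the plots is inferred from the undivided PK population and one geometric mean per dose. Individual values are shown too, no formal test of dose proportionality is planned, and with no exposure difference nothing shifts. A reader might infer that dose proportionality is distorted; the documents support only that it can be confounded.
- **72 is a ceiling.** Cohorts are up to 30, lead-ins may be as small as 3, and combination doses may move in either direction. Only patients with sufficient data enter the parameter population. Nine single-agent patients at 10 mg/kg would be expected chiefly if that were the MTD, when Section 2.2.1 allows a lower combination dose to be considered. Cohort 3 would add single-agent patients if it ran at the shared dose. The percentages are therefore not the expected PK mix.
- **Dose group is undefined.** It might be meant to include cohort, and Section 8.3 does mention treatment groups when suppressing statistics. The plain by-dose wording elsewhere points the other way, and if cohort is intended the SAP should say so.

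**Conclusion.** The point holds for the planned summaries. As written, the SAP combines single-agent and combination patients at any shared dose, and no planned summary reports PK for either combination, although a Part 2 secondary objective asks for it. This rests on stated grouping rules rather than on detail left to the protocol. If combination doses move, the overlap moves to whatever dose is shared.

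The second part is conditional. The 10 mg/kg geometric mean can be confounded with regimen and population, but size and direction depend on an exposure difference that the SAP does not give. The shifts to 0.81 and 1.24 follow only from the assumed ratios of 0.8 and 1.25. The shares of about 3-5%, or 11% with nine single-agent patients, are enrolment bounds under full cohorts, lead-ins of 6, no dose change and complete PK evaluability.

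The plan should be corrected before the tables are programmed. Nothing here affects data collection.

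**What to change.** In Sections 7.3 and 9.2.2.2:

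- Summarise PK parameters and concentrations by regimen within dose and cycle, with three groups: single agent (including Cohort 3), plus 7+3, and plus hypomethylating drug.
- Limit the dose-normalised plots and the accumulation-ratio ANOVA to single-agent data. Alternatively, mark regimen in the plots and add it as a term in the ANOVA.
- Define dose group, and say whether it includes regimen.

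Separating decitabine from azacitidine is optional, because the objective treats them as alternatives.

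The cost is more table columns and smaller cells. In small cells the rule in Section 8.3, which suppresses statistics when more than half the values are not calculable, may apply more often. No new data are needed.
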